Second-Generation Magnetically Controlled Capsule Gastroscopy with Improved Image Resolution and Frame Rate: Study Protocol for A Randomized Controlled Clinical Trial

Document Date: February 1st, 2019.

Trial registration: ClinicalTrials.gov ID: NCT03977935

INTRODUCTION

Magnetically controlled capsule gastroscopy (MCCG) provides good visualization of the stomach, and is highly accepted due to the characteristics of painlessness, noninvasiveness and favorable diagnostic accuracy as conventional endoscopy^{1,2}. However, the upper gastrointestinal (UGI) tract under capsule endoscopy (CE) continues to present challenges including rapid transit through esophagus and duodenum^{3,4}, as well as longer gastric examination time⁵ compared to conventional endoscopy. Technical improvements in frame rate, field of view, dual camera, image resolution and battery life have been performed to optimize the clinical application of CE, and some turned out to be effective^{6,7,8,9}.

Therefore, a new-generation MCCG (MCCG-2) highlighted with a higher and adaptive frame rate of 8 frames per second (fps), better image resolution of 720 x 720 pixels, wider field of view of 150°, extended battery life of more than 12 hours and anti-jamming wireless data transmission has been developed. Hence, this pilot study was conducted to determine whether MCCG-2 can further optimize the visualization of UGI tract, thus result in better diagnosis of UGI diseases.

METHODS

Study design

This pilot study was a prospective, single-centered, blinded randomized controlled study, approved by the institutional review board of Shanghai Changhai Hospital and registered at ClinicalTrials.gov. with registration number NCT03977935. Written informed consent was obtained from each enrolled subject.

Patients

From May 2019 to June 2019, 80 consecutive patients aged 18-80 years with or without abdominal complaints referring for MCCG examination were prospectively enrolled and randomly allocated into MCCG-1 group or MCCG-2 group a 1: 1 ratio. Patients with any of the following contraindications for MCCG were excluded: pacemakers or electromedical devices implanted which are incompatible with magnetic field; suspected or known gastrointestinal stenosis, obstruction or other known risk factors for capsule retention; scheduled magnetic resonance imaging examination before excretion of capsule; pregnancy or suspected pregnancy; and any other contraindications determined by endoscopists.

Study intervention

The MCCG, a robotic magnetic capsule guidance system, was provided by Ankon Technologies Co. Ltd (Shanghai, China). The MCCG system was consisted of a guidance magnet robot, a capsule endoscopy, a data recorder and a computer workstation with a software for real-time view and two joysticks for capsule orientation control. The guidance magnet robot was of C-arm type with five degrees of freedom: two rotational (horizontal and vertical directions) and three translational (forward/backward, up/down, left/right).

After a standardized gastrointestinal (GI) preparation regimen for MCCG, patients were placed in the left lateral decubitus position and swallowed MCCG-1 or MCCG-2 with a small amount of water according to a random number table with the help of nurses at the digestive endoscopic center. When MCCG reached the stomach, it would be lifted away from the posterior wall, rotated and advanced to the fundus and cardiac regions, followed by the gastric body, angulus, antrum and the pylorus. During this procedure, position changes such as supine, prone, left and right lateral were also helpful in achieving clear observation and smooth transition. Standardized examination procedure of MCCG was available online at videogie.org¹⁰. Cases with suspected malignancy were rechecked under conventional endoscopy.

Image capture rate in the esophagus and stomach were 2 fps or 6 fps in MCCG-1 or MCCG-2 group, and standardized operation of MCCG were performed twice for complete gastric examination. After the capsule moved into the duodenum, patients left the hospital with the data recorder to continue with small-bowel examination. In the small bowel, MCCG-2 offered an adaptive frame rate technology which adjusted the image capture rate based on how fast the capsule was moving.

Study outcomes and definition

Basic characteristics of the enrolled patients were prospectively collected. Primary study outcome was efficacy analysis including visualization of the esophagus and duodenum indicated by detection rate of Z-line and duodenal papilla defined as at least one image of Z-line or duodenal papilla was obtained, the number of images captured for esophagus and Z-line, circumferential visualization of Z-line as the number of quadrants observed and cleansing level of Z-line as bubbles/saliva on Z-line¹¹. Operation related parameters included esophageal transit time (ETT), gastric examination time (GET), gastric transit time (GTT), small bowel transit time (SBTT) and total running time (TRT). Image quality,

maneuverability and detection of lesions were also prospectively documented. Any procedure related adverse events were closely recorded.

GET was defined as the time for examination of gastric primary anatomical landmarks twice. Image quality ranged from one to ten denoting from the worst to the highest¹². Maneuverability was classified as fluency (the response to operation and video effect), stability (the ability of holding the capsule at one position for at least one minute) and comfortableness (the operator's fatigue degree during the examination), and each index graded from one to five with one as the worst and five as the best.

All examinations and maneuverability evaluation were performed by an endoscopist ([name]) with an experience of more than 1000 cases of MCCG operation. Two other endoscopists blinded to the grouping would independently evaluate the image quality with a mean value as the final score, and a third endoscopist would make the final judgement when there existed a discrepancy more than three. The randomization schedule was generated by the investigator using a random number table, making it possible that patients enrolled and endoscopists involved were all blinded to the treatment protocol assigned.

Statistical analysis

As a pilot study to evaluate the clinical utility of MCCG-2, sample size was not calculated for this study. Quantitative data were summarized with parametric statistics, mean and standard deviation, or with nonparametric statistics, median and interquartile range, whereas categorical data were presented as frequency (percentage). Data with a normal distribution were compared using parametric analysis and non-normally distributed data were compared using nonparametric statistical analyses. Categorical variables were analyzed with the χ^2 exact test and quantitative data were analyzed using the Mann–

Whitney Wilcoxon test with a final two-sided P value of less than 0.05 indicating statistical difference.

SPSS 13.0 software was used.

Central contact:

[name]

National Clinical Research Center for Digestive Diseases; Department of Gastroenterology,

Changhai Hospital, [name]

[contact]

[contact]

E-mail: [name]

Disclosures: The authors declared **no** conflict of interest.

Acknowledgement: None.

REFERENCES

7. Monteiro S, de Castro FD, Carvalho PB et al. PillCam® SB3 capsule: Does the increased frame rate eliminate the risk of missing lesions? *World J Gastroenterol* 2016; 22: 3066-3068.

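### The lesion-detection comparison, a non-primary outcome, ignores abdominal-complaint status although patients with and without complaints are pooled; a stratified analysis is a minor, nearly free gain in precision

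*Combined protocol and SAP*

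**What the plan says.** The Patients section treats the study population as one group: "80 consecutive patients aged 18-80 years with or without abdominal complaints referring for MCCG examination were prospectively enrolled". The same sentence says they were "randomly allocated into MCCG-1 group or MCCG-2 group a 1: 1 ratio". Under Study outcomes and definition, the method of allocation is given as "The randomization schedule was generated by the investigator using a random number table". No strata, blocks or minimization are described there or under Study intervention.

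That section defines the primary outcome by visualization: "Primary study outcome was efficacy analysis including visualization of the esophagus and duodenum indicated by detection rate of Z-line and duodenal papilla", followed by image counts, quadrants of the Z-line seen, and cleansing. Lesions come afterwards, among further outcomes: "maneuverability and detection of lesions were also prospectively documented". It is not stated whether lesions are counted per patient or per lesion. On baseline data the section says only "Basic characteristics of the enrolled patients were prospectively collected". Complaint status is not named among them, and no use of them in the analysis is given.

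Under Statistical analysis, "Categorical variables were analyzed with the χ^2 exact test", with a "two-sided P value of less than 0.05 indicating statistical difference". No covariate, stratum or subgroup is mentioned. The study is presented as a pilot without a sample size calculation.

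**The concern.** Each patient swallows one type of capsule, and only suspected malignancies are rechecked by conventional endoscopy. For most patients there is therefore no independent count of the lesions present. The number of patients with a lesion found in an arm reflects both how well the capsule shows lesions and how many patients in that arm have one to show.

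Complaint status is a case-mix variable that the protocol itself names, and it is known before allocation. If it predicts lesions, an unadjusted comparison has two drawbacks. Variation between symptomatic and asymptomatic patients remains in the error term. And if one arm happens to receive more symptomatic patients, the excess feeds directly into the observed difference. The Introduction links better visualization to better diagnosis, so readers will look at the lesion result even though it is not primary.

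**Working it through.** The plan has no figure of its own to reproduce: 80 patients are given without power, effect size or lesion rates.

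**Inputs.** From the documents: N = 80, 1:1 allocation, unadjusted test, two-sided 0.05. Assumed: an exact 40/40 split (the plan does not say that it is forced), half of patients with complaints (30% and 70% as a check), and the lesion rates shown in the table.

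**1. How large is a chance imbalance?** Let X be the number with complaints in one arm, when 40 of the 80 have complaints. X is hypergeometric (80, 40, 40), and the between-arm difference in share is (2X − 40)/40.

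- SD = (2/40) × √(40 × 0.5 × 0.5 × 40/79) = 0.05 × 2.25 = 0.1125, or about 11 points.
- A difference of at least 10 points means |X − 20| ≥ 2: probability 0.503.
- A difference of at least 20 points means |X − 20| ≥ 4: probability 0.117.
- With a complaint share of 30% or 70%: SD 0.103, probabilities 0.465 and 0.087.
- Treating the arms as two independent binomials with half symptomatic: about 43% and 9%.

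**2. What does it do to the lesion comparison?** With lesion rates pc (complaints) and pn (none) and half symptomatic, p = (pc + pn)/2. Total variance is p(1 − p). Within-stratum variance is 0.5[pc(1 − pc) + pn(1 − pn)]. SE = √(2 × variance/40). The shift from a 20-point imbalance is 0.20 × (pc − pn). Equivalent N is 80/(1 − reduction).

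| pc / pn (assumed) | Total variance | Within strata | Reduction | SE, unadjusted to stratified | Shift at 20-point imbalance | Equivalent N |
|---|---|---|---|---|---|---|
| 60% / 20% | 0.2400 | 0.2000 | 16.7% | 0.110 to 0.100 | 8 points | 96 |
| 60% / 30% | 0.2475 | 0.2250 | 9.1% | 0.111 to 0.106 | 6 points | 88 |
| 50% / 30% | 0.2400 | 0.2300 | 4.2% | 0.110 to 0.107 | 4 points | 83.5 |
| 40% / 30% | 0.2275 | 0.2250 | 1.1% | 0.107 to 0.106 | 2 points | 80.9 |
| equal rates | – | – | 0 | no change | 0 | 80 |

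**3. Is the false-positive rate affected?** By exact enumeration over all 40/40 randomizations, for complaint shares of 30% to 70% and a range of lesion rates, the unadjusted Pearson test rejects in 4.8% to 5.6% of null trials and Fisher's test in 2.8% to 3.2%. At 60/20 with half symptomatic, Pearson gives 5.2%. With a 30% lesion rate and no prognostic effect, the values are 4.8% and 2.8%, so there is no material inflation.

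Given that a 20-point imbalance has occurred (half symptomatic), Pearson gives 9.4%, 8.0%, 6.3% and 5.2% for the first four rows of the table, and Fisher 5.8%, 4.9%, 3.7% and 3.0%. At a 10-point imbalance Pearson is 4.8% to 5.3% in the first three rows.

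**4. What does stratifying buy?** Power for an assumed true difference of 20 points (normal approximation, half symptomatic) goes from 45.0% to 45.4% at 40/30, 44.7% to 46.2% at 50/30, 45.0% to 48.8% at 50/20, and 45.0% to 57.1% at the extreme 60/10. In simulation, the two analyses had power of 46.6% and 46.8% when complaints carried no information.

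**5. Would stratified allocation alone do it?** No. With balanced strata and the test unchanged, the test becomes conservative: at 50/20, Pearson 3.8% and Fisher 2.1%. The gain comes only if the analysis uses the stratum.

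**The case against.** The strongest reply is that chance imbalance in a randomized trial is ordinary sampling error. Its expected value is zero, and the planned test already allows for it. That stands, as step 3 shows. A reader might infer that pooling the two kinds of patient biases the lesion comparison or inflates false positives; the plan as written does neither. What remains is a concern conditional on the split that occurs, plus some lost precision.

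Second, nothing in the documents shows that complaint status predicts lesions, and the whole effect depends on that. This also stands. Under mild or moderate contrasts the gain is a few percent of variance. Age, with a range of 18 to 80, could be prognostic too. The case for complaint status is only that the protocol names this mix itself.

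Third, a reader might take lesion detection to be the one outcome that speaks to diagnosis, and so treat this as a threat to the trial's main result. The documents do not support that. The aim is stated through visualization, the primary outcome is about the Z-line and papilla, and lesions are an additional outcome in a pilot. Nothing here touches the primary analysis.

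These points limit the weight of the concern. They do not argue against an adjustment that costs almost nothing.

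**Conclusion.** The concern holds in a limited form and is minor. Complaint status is used in neither the allocation nor the lesion comparison, so a realized imbalance would stay in the estimate and some precision may be given up. Imbalances of 10 points or more are about as likely as not at 40 per arm, but under moderate lesion-rate contrasts they move the difference by only a few points, against a standard error of about 11. The benefit of stratifying runs from zero, if complaints are not prognostic, to a variance cut of about 17% at 60/20. The complaint share, the lesion rates and the 40/40 split are all assumptions.

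A reader might also conclude that the randomization is defective because it is not stratified. That does not follow: unstratified allocation is valid, and stratifying it without changing the test would gain no precision.

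**What to change.** Add one sentence to Statistical analysis: lesion detection is compared per patient (at least one upper gastrointestinal lesion, yes or no) with a Mantel-Haenszel risk difference and test stratified by abdominal complaints (yes/no). Name the exact form of the test, since at 40 per arm the score and Wald versions differ slightly in error rate and power. Report complaint status by arm in the baseline table.

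Fix this before lesion results are seen by arm, so that the adjustment is not chosen in response to an observed imbalance. The Patients section describes enrolment in the past tense; if results have already been seen, present the stratified analysis as a post hoc sensitivity analysis.

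The cost is one recorded baseline variable, with essentially no loss of power if it is not prognostic. Separate blocked allocation lists by complaint status are optional, make sense only if allocation is still open, and are worthwhile only together with the stratified analysis.

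### Six primary measures share one unadjusted P<0.05 with no success rule, and one of them, the esophageal image count, largely restates the frame-rate setting

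*Combined protocol and SAP*

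**What the plan says.** All references are to the combined protocol and SAP.

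- **Study outcomes and definition** opens: "Primary study outcome was efficacy analysis including visualization of the esophagus and duodenum indicated by detection rate of Z-line and duodenal papilla". Detection is "defined as at least one image of Z-line or duodenal papilla was obtained". The same sentence goes on to "the number of images captured for esophagus and Z-line" and "circumferential visualization of Z-line as the number of quadrants observed and cleansing level of Z-line as bubbles/saliva on Z-line". The named measures are therefore Z-line detection, papilla detection, esophageal image count, Z-line image count, Z-line quadrants and Z-line cleansing.
- **Statistical analysis** gives one criterion for every comparison: "two-sided P value of less than 0.05 indicating statistical difference". It mentions no adjustment, order, composite or rule for success. It also says: "As a pilot study to evaluate the clinical utility of MCCG-2, sample size was not calculated for this study".
- **Study intervention** fixes the device settings: "Image capture rate in the esophagus and stomach were 2 fps or 6 fps in MCCG-1 or MCCG-2 group".
- **Introduction** gives the aim: "this pilot study was conducted to determine whether MCCG-2 can further optimize the visualization of UGI tract". It also headlines 8 fps for MCCG-2, whereas Study intervention gives 6 fps in the esophagus and stomach.

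**The concern.** The aim is a yes-or-no question about visualization, but nothing links the six results to an answer. Two gaps follow.

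First, the esophageal image count is frame rate multiplied by time in the esophagus. The frame rate differs by design, so the count will differ even if MCCG-2 shows no additional landmark. A report that followed the plan could give a significant primary result that says little beyond the device specification.

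Second, the remaining measures are tested side by side without error control, and mixed results have no agreed reading. If Z-line detection improves and papilla detection does not, the plan does not say what that means. The study is called a pilot, but no sentence says that the comparisons are exploratory or limits what a P value below 0.05 supports.

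**Working it through.** The plan gives no power, effect size or expected rates, so there is no figure of its own to reproduce.

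**Inputs from the document.** 80 patients at 1:1, so 40 per arm; 2 and 6 fps in the esophagus; two-sided 0.05; Mann–Whitney for quantitative data and a chi-square exact test for categorical data.

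**Assumed, because the document gives no values.** Transit-time distribution, Z-line dwell time, proportion of patients with the Z-line in view, and correlations between tests.

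**1. Expected ratio of esophageal counts.** Count ≈ fps × transit time. At equal transit time the ratio is 6/2 = 3. If the 8 fps headline applied in the esophagus, it would be 8/2 = 4.

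**2. Chance that frame rate alone gives P<0.05 for the esophageal count.** Take the same log-normal transit-time distribution in both arms, with standard deviation s on the log scale. The normal approximation is Φ(ln 3 / (s√(2/40)) − 1.96), with ln 3 = 1.0986 and √(2/40) = 0.2236. The simulation sets count = floor(fps × time) + 1 and applies Mann–Whitney, with 10,000 trials at each of the median transit times 5, 10 and 60 s.

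| s | Normal approximation | Simulated Mann–Whitney, across medians |
|---|---|---|
| 1.0 | Φ(4.91 − 1.96) = 0.998 | 0.996 to 0.998 |
| 1.2 | Φ(4.09 − 1.96) = 0.984 | 0.975 to 0.976 |
| 1.5 | Φ(3.28 − 1.96) = 0.906 | 0.881 to 0.889 |

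A multiplicity correction does not change this much. At Bonferroni's 0.05/6 = 0.00833, the normal approximation still gives 0.989 at s = 1.0 and 0.738 at s = 1.5.

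**3. Z-line image count.** Set the count to 0 if the Z-line is not in view, otherwise max(1, round(fps × dwell time)), with the same proportion in view in both arms. The max(1, …) rule holds detection equal between arms by construction. Simulated chance of P<0.05 at an assumed median dwell of 1 s:

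| In view | log-SD 1.0 | log-SD 1.5 |
|---|---|---|
| 30% | 0.071 | 0.059 |
| 50% | 0.206 | 0.117 |
| 70% | 0.573 | 0.305 |
| 90% | 0.950 | 0.681 |

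With a median dwell of 0.3 s and log-SD 1.0, the figures at 70% and 90% in view fall to about 0.39 and 0.85. The result is governed by quantities that the document does not give.

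**4. The other four measures, all nulls true.** Chance of at least one two-sided P<0.05:

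- Independent tests at nominal size: 1 − 0.95⁴ = 0.185.
- Equicorrelated normal tests at nominal size: 0.156, 0.115 and 0.093 at correlations 0.5, 0.8 and 0.9.
- If the chi-square exact test is taken to be Fisher's, its size at true detection rates of 95% is 0.0040 per test. Two such tests and two at 0.05 give 0.070 at correlation 0.9 and 0.105 if independent.
- In favour of MCCG-2 only, at nominal size: 1 − 0.975⁴ = 0.096 if independent, 0.046 at correlation 0.9, against 0.025 for a single test.

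Three of these four measures describe the same Z-line, so the independent end is unlikely.

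**5. What 40 per arm can show on detection.** Newcombe 95% intervals for the difference are −0.014 to 0.390 (observed 50% vs 70%), −0.001 to 0.381 (60% vs 80%) and 0.023 to 0.366 (70% vs 90%). Fisher power at 0.05, if those were the true rates, is 0.368, 0.408 and 0.534.

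**The case against.** The strongest reply is that this is a declared pilot, and that the threshold is said to indicate a statistical difference, not success or superiority. Strict familywise control in a study with no sample-size basis would be partly a matter of taste. This stands, and it lowers the severity. It does not supply the missing sentence that the comparisons are exploratory.

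A second reply is that the plan does point to a lead. Visualization is said to be indicated by the two detection rates, with counts, quadrants and cleansing following. That reading is plausible, so it would be too strong to infer that the plan gives no hint of priority. But the sentence does not clearly separate the detection rates from the rest, and it gives no order between the two.

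A third reply is that more frames of a fast-transit organ is what the device is for. This also stands. A reader might take the 88% to 99% figures as a false-positive rate. They are not: they are the power to detect a real device difference. Frame rate may also improve detection itself, since one image suffices. The narrow point remains that a higher count does not by itself show that more landmarks were seen.

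A reader might also infer that the Z-line count is just as automatic, or that the six tests carry the full 1 − 0.95⁶ = 26.5% error. The document supports neither. The first depends on undocumented in-view and dwell-time values. The second assumes six independent tests with true nulls, although frame rate acts directly on both counts and the Z-line measures are related.

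**Conclusion.** The point holds at minor to moderate severity. The text establishes six named measures, one unadjusted threshold and no success rule. The 3-fold expected ratio follows from the stated 2 and 6 fps and assumes similar transit times, which randomization makes reasonable. The 88% to over 99% range rests on log-normal transit times with log-SD 1.5 to 1.0. The 9% to 19% range for the other four measures rests on assumed correlations from 0.9 to 0 at nominal test size. It drops to about 7% only if the categorical test is Fisher's, true detection rates are near 95% and correlation is about 0.9. Confidence is high in what the text says, and lower in the size of the assumption-driven figures.

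It would go too far to conclude that the trial will claim success on an image count. The plan permits that reading but does not state it.

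**What to change.** 1. Report the esophageal and Z-line image counts descriptively, outside the efficacy claim.
2. Base the visualization conclusion on Z-line and papilla detection, with quadrants and cleansing as supporting measures.
3. State that in this pilot these are exploratory between-group differences with 95% confidence intervals, and that no superiority claim follows from a single P<0.05.
4. Reconcile the 8 fps in the Introduction with the 6 fps in Study intervention. The latter describes adaptive capture only for the small bowel, which may explain the difference, but the document does not say so.
5. The document is dated February 2019, yet it describes enrolment in May to June 2019 in the past tense. If unblinded data have already been seen, say openly that the limits in items 1 to 3 were added afterwards.

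The cost is wording only, with no added patients or procedures. The sponsor gives up an unqualified significant primary result, and the intervals will be wide: about −1 to 39 percentage points for observed rates of 50% and 70%. Making one detection rate confirmatory instead would not rescue the claim at this size, since Fisher power is only 37% to 53% for the 20-point differences shown above.

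### SBTT is compared between arms with no rule for examinations still in the small bowel when recording ends; if MCCG-1 records for a clearly shorter time and only finished cases are analysed, identical transit would look longer with MCCG-2

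*Combined protocol and SAP*

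**What the plan says.** The Study outcomes and definition section names five operation related parameters: ETT, GET, GTT, and "small bowel transit time (SBTT) and total running time (TRT"). They are listed apart from the primary outcome, which concerns visualization of the esophagus, Z-line and duodenal papilla. Only one of the five is defined: "GET was defined as the time for examination of gastric primary anatomical landmarks twice".

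The Study intervention section says that once the capsule is in the duodenum, "patients left the hospital with the data recorder to continue with small-bowel examination". The Introduction gives MCCG-2 an "extended battery life of more than 12 hours". No battery life is given for MCCG-1, and no time is given for return of the recorder.

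The Statistical analysis section says "Data with a normal distribution were compared using parametric analysis and non-normally distributed data were compared using nonparametric statistical analyses", and then that "quantitative data were analyzed using the Mann"–Whitney Wilcoxon test at two-sided 0.05. The document contains no censoring rule, exclusion rule, analysis set or completion outcome for the small bowel.

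**The concern.** Because the patient has gone home, the end of small-bowel transit has to be read from the recording. If recording stops while the capsule is still in the small bowel, SBTT has not been observed; all that is known is that it exceeds the time recorded. Neither a t-test nor a Mann-Whitney test on observed values can take in that information. The analyst has to drop the case, enter the end of recording as if it were the value, or rank the case as longest. All three are compatible with the plan as written, and they can give different answers.

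The gap may not be even between the arms. Battery life is one of the features by which MCCG-2 is presented as an improvement, so the device under test may itself determine which long transits can be seen. Dropping unfinished cases would then remove long values mainly from MCCG-1. A significant SBTT difference could reflect recording length and be misread as an effect on transit.

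**Working it through.** The plan gives no SBTT figure, power or sample-size calculation, so there is no figure to reproduce. The check asks how often identical transit would be declared different.

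**From the document.** "80 consecutive patients aged 18-80 years", "randomly allocated into MCCG-1 group or MCCG-2 group a 1: 1 ratio": 80 / 2 = 40 per arm. Two-sided 0.05. MCCG-2 recording limit taken as 12 h.

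**Assumed.** SBTT (S) is log-normal with median 5 h and log-SD 0.35 or 0.5, the same in both arms. Time before the small bowel (G) has median 1 h (log-normal, log-SD 0.4) and is independent of S. The MCCG-1 limit L is 8, 9, 10 or 12 h. An examination is finished if G + S ≤ L.

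**Check by hand.** Fix G at 1 h and take log-SD 0.5.
- Unfinished share = 1 − Φ(ln((L − 1)/5)/0.5).
  - L = 8: ln(7/5)/0.5 = 0.673, giving 25%.
  - L = 12: ln(11/5)/0.5 = 1.577, giving 6%.
- Median of finished cases = 5 × exp(0.5 × Φ⁻¹(p/2)), where p is the finished share.
  - L = 8: p/2 = 0.375, Φ⁻¹ = −0.319, giving 4.26 h.
  - L = 12: p/2 = 0.471, Φ⁻¹ = −0.072, giving 4.82 h.

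The true median is 5 h in both arms. Finished cases alone show a difference of 4.82 − 4.26 = 0.56 h, produced entirely by the recording limit. Simulation with G varying gives 26% against 6% unfinished (about 10 against 2 of 40) and medians of about 4.2 and 4.8 h.

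**Simulated false-positive rates, finished cases only, Mann-Whitney (t-test).** Ranges reflect repeated runs.

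| MCCG-1 limit | log-SD 0.35 | log-SD 0.5 |
|---|---|---|
| 8 h | 22-23% (33-36%) | 30-32% (45-47%) |
| 9 h | 9-10% (13-15%) | 14-16% (21-24%) |
| 10 h | 6% (7%) | 8% (10-11%) |
| 12 h | about 5% (5%) | about 5% (5%) |

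At 8 h with log-SD 0.5, nearly all significant results point to longer SBTT with MCCG-2 (0.305 of 0.306).

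**Sensitivity to assumed transit, 8 h limit.** With SBTT median 4 h and log-SD 0.35 the Mann-Whitney rate is about 7%. Over a wider grid (median 4 to 6 h, log-SD 0.35 to 0.5, 1 to 1.5 h before the small bowel) it reaches 70%, but that extreme needs 44% against 6% unfinished.

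**Other ways of handling unfinished cases.**
- End of recording entered as the value (SBTT median 5 h): same direction, Mann-Whitney about 6-8% at 8 h.
- Ranked longest without a common window: the direction reverses. The rate clearly exceeds 10% only at 8 h with SBTT median 6 h (13-30%).
- Common recording end in both arms at 8, 9 or 10 h: about 5%.
- Log-rank with censoring at end of recording, or Mann-Whitney over a common window: about 4-6% throughout.

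**The case against.** The strongest objection is that the document does not establish the bias. Its only anchor is the word for an extended battery, which suggests a direction but no gap. MCCG-1 battery life, recorder return time and the transit distribution all come from outside, and across those assumptions the result runs from no bias to a large one. A material effect needs an MCCG-1 limit near 8 or 9 h. This stands, and it is why the point is conditional.

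A reader might infer that the plan analyses finished cases only, so that the SBTT comparison is biased as planned. The document does not say so. Dropping unfinished cases is one reading of a silent plan. Entering the end of recording instead largely removes the effect by Mann-Whitney.

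A reader might also take the 8 h, log-SD 0.5 result as typical. It uses the larger of the two assumed spreads; the smaller one gives lower rates at 8, 9 and 10 h.

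Finally, SBTT is not a primary outcome, the study is a pilot aimed at the upper gastrointestinal tract, and a large bias would come with an imbalance in unfinished counts. That limits the consequence. The imbalance would help a reader only if the counts were reported, and the plan does not call for them.

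**Conclusion.** The omission stands without any assumption: SBTT is undefined, and no rule covers an examination that is unfinished when recording ends, although the named tests need a complete value.

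The bias is conditional. It requires (a) a clearly shorter MCCG-1 battery, (b) recording to battery end in both arms, and (c) analysis of finished cases only. Under all three, and with the assumed transit times, it is material at an MCCG-1 limit of 8 h, modest at 9 h, small at 10 h and absent at equal limits. If (b) fails because a common return time ends recording in both arms, it disappears. If (c) fails and the end of recording is used as the value, little remains in the Mann-Whitney comparison.

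Severity is minor. The document does not support a claim that the SBTT result is biased, or that any primary visualization outcome is touched.

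**What to change.** - Define the start and end of ETT, GTT and SBTT, and define TRT.
- State before analysis how unfinished examinations are handled. Either of two methods would do. (1) Among patients whose capsule enters the small bowel, analyse SBTT as time-to-event censored at end of recording, with Kaplan-Meier medians and a log-rank test. (2) Use Mann-Whitney over a recording window common to both arms, with unfinished cases ranked longest.
- Report the number of unfinished small-bowel examinations by arm.

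**Cost.** A few lines of text and a little extra analysis. If TRT runs from swallowing to end of recording, and ETT and GTT together cover the time up to small-bowel entry, the censoring time is TRT − ETT − GTT and no new data are needed. None of the three is defined, so this has to be confirmed.

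**Limits.** Log-rank assumes that end of recording is unrelated to small-bowel transit. The common window discards late recording in the longer-battery arm. Precision is barely affected at an 8 h limit with SBTT median 5 h and log-SD 0.5 (SD of the median 0.497 h by Kaplan-Meier against 0.492 h with complete data). With 46% unfinished, however, the median could not be estimated in about 10% of simulated arms.
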